Once a subject is identified a page will be sent to a member of the research team (i.e. ED screener, research staff member, GI fellow on call, or GI attending on call) from the ED. In addition to this, the clinical research coordinator and or GI fellow will screen the Emergency Department triage software for patients who are listed as having NHGIB. Based on prior experience Ref Sachdev we expect for every 3 patients asked to participate in the study, there will be 1 patient who agrees to participate. In the emergency department study already cited, the Emergency Department at UMass sees about 350 patients annually for GI bleeding. Of these patients, approximately 230 patients have NHGIB. Given the 3:1 screening ratio, we would expect approximately 75 NHGIB patients every year to agree to participate in the study. In 24 months, we would expect to recruit up to 160 patients to our study.

INVESTIGATOR STUDY PLAN - REQUIRED

Once a subject is identified the subject will then be seen and examined by the GI fellow and attending as per standard of care and asked to participate in the study

Randomization

If inclusion/exclusion criteria are met, the consent discussion takes place and only if the subject agrees and consent is obtained, then the subject is randomized to the “Early Capsule Group” or “Conventional workup Group.” All patients in the “Early Capsule group” will receive the video capsule. Only some of the patients in the “Conventional Workup Group” will receive the capsule as indicated by what is considered the standard workup.

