We will assign patients to study ID numbers consecutively by the order of which they are enrolled in our study. For the Randomization Process we will be utilizing a random sorting generator to assign integers in a random order, corresponding to study IDs which allows researchers to randomly assign study participants into specific study groups. Assignments are put into a mail merge, locked with a password, and printed, then put into a sealed, security envelope, which is sealed with a Study ID sticker. The Randomization Scheme will allow us to attach particular Study ID numbers randomly to particular groups based on our criteria to have 80 subjects in the early capsule group and a comparable number in the conventional workup group. The envelope is only opened once all entry criteria have been met and the subject will be assigned a group. Subjects with a Study ID ending in 1-100 will be enrolled at University Campus. Subjects with a Study ID ending in 101-120 will be enrolled at Memorial Campus. Subjects with a Study ID ending in 121-160 will be enrolled at either campus, depending on enrollment. Enrollment will be competitive at the two locations and there is no specific quota to be reached at either location.

We plan to enroll up to 160 subjects in our study. 80 subjects will be randomized to the “early capsule” deployment group. This means that this group of subjects will have a VCE deployed as soon as possible after presentation to the ED, once the consent process has taken place, eligibility has been confirmed, and the subject has met the standard of care guidelines for preparation before capsule ingestion. Standard preparation for capsule ingestion means that a patient cannot eat for 10 hours prior to deployment of the capsule. Therefore, patients in our study will be asked when they had last eaten. If patients report that they have not eaten anything over the past 10 hours we will deploy the capsule immediately. If, however, patients say that they have eaten something over the past 10 hours we will take note of when they believe they last ate and will deploy the capsule 10 hours after the time that they last ate. In the pilot [Sachdev] study all patients in the early capsule arm received the capsule within a mean of 4 hours of admission to the ED, and none had food in the stomach on capsule examination.

INVESTIGATOR STUDY PLAN - REQUIRED

Procedure

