Depending on the findings a recommendation will be made as to the next most appropriate test. See attached Figure 1. If blood is found in the esophagus, stomach or duodenum an upper endoscopy is recommended. If blood is seen in the small intestine, it will be recommended that the subject next have a push enteroscopy, deep enteroscopy, or angiography. If blood in right colon, colonoscopy may be performed or deferred to colonoscopy as an outpatient, if active bleeding has ceased. If the capsule study is not diagnostic and no blood is seen in the GI tract and there is no ongoing hematochezia, the subject will be placed in ED observation for up to 23 hours and evaluated for potential discharge and follow-up by gastroenterology as an outpatient.

INVESTIGATOR STUDY PLAN - REQUIRED

If no bleeding/ blood or a likely source is found. These individuals will be considered for observation, early discharge and follow up in the GI outpatient setting.

For most subjects, the capsule will pass in a bowel movement within 24 - 72 hours of ingestion.

An equal number subjects [up to 80] will be randomized to the “conventional workup group”. “Conventional Workup” for NHGIB could include upper endoscopy, colonoscopy, and additional capsule or small bowel enteroscopy depending on the subject’s presentation and the results of the workup performed by the gastroenterology team. For some subjects, the VCE would be done as part of standard of care estimated that 5-15% of patients will have small intestinal bleeding. For patients requiring a video capsule endoscopy as part of “conventional workup” the patients will be given the same Olympus video capsule that is used in the “Early Capsule” group. Further management would be as standard of care. These subjects will be discharged on the recommendation of the attending hospitalist after completion of treatment.

Review and Follow-Up

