Throughout course of a study subject's participation in the study they will be followed for signs of adverse events to medication administration or for complications of capsule endoscopy. Adverse events will be documented as part of initial data analysis. This data analysis will be performed by the residents and fellows who are part of the study staff for this project.

Given that we anticipate minimal adverse events, any adverse events that occur will be reviewed by the study staff and the Primary Investigator within one week. This would include a complete analysis of the how the adverse event occurred in order to help prevent further events going forward. At that time the Primary Investigator will also assess cumulative reports.

14) Withdrawal of Subjects*

If the patient is unable to swallow the capsule we would remove them from the study.

Patients will be withdraw from study if the bleeding source is found to be outside of the stomach or intestines.

A subject can withdraw from the study at any time per their request.

15) Risks to Subjects*

This study is investigating the benefits of re-ordering the process of the current care algorithm for NHGIB. Video capsule endoscopy is already part of standard of care for many GI bleeding workups. This is not a new diagnostic modality and no new risk is being introduced from this technology itself. There are no anticipated risks to subjects who are randomized to the early deployment of the capsule and the diagnostic yield is expected to be at least comparable to the standard deployment.

One anticipated risk is a breach of confidentiality and to minimize this risk all identifiers will be destroyed. In order to minimize this risk, as described in question 12, identifiers will be destroyed. Data collected will be analyzed using study ID numbers only.

The most significant risk of VCE is capsule retention. This risk is the same for both groups and there is no anticipated unforeseen risk with early deployment. The risks do not change based on timing. Capsule retention is when the video capsule does not complete its transit throughout the GI tract. Studies have varied in their reports of the frequency of capsule retention with rates of about 1%, ranging from 1-13% of total cases. The

INVESTIGATOR STUDY PLAN - REQUIRED

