Another potential risk to the subjects in the study relates to the prokinetic medications (metoclopramide and erythromycin) which would be given if the capsule is slow to leave the stomach. Risks associated with the use of metoclopramide include allergic reactions (e.g., skin rash or difficulty breathing), extrapyramidal reactions, central nervous system effects (e.g. insomnia, headache, confusion), neuroleptic malignant syndrome, endocrine disturbances (e.g. galactorrhea, amenorrhea, gynecomastia), and cardiovascular effects (e.g. hypotension, tachycardia, bradycardia, heart failure, and AV block). The adverse effects of metoclopramide are directly correlated to the duration and dose of the drug given, so we expect the incidence of adverse effects to be minimal given that we are giving one dose only for the purpose of this study. For erythromycin, adverse effects include allergic reactions (e.g., skin rash or difficulty breathing), gastrointestinal effects (including nausea, vomiting, abdominal pain, diarrhea, and anorexia), hepatic dysfunction, pseudomembranous colitis, QT prolongation, and ventricular tachycardia.

These drugs are frequently used in patients with upper GI bleeding to help empty the stomach of clot prior to endoscopy to enhance visualization of the bleeding site(s). Single doses of these drugs have very low risk

INVESTIGATOR STUDY PLAN - REQUIRED

16) Potential Benefits to Subjects*

Subjects who receive the early capsule deployment may have a quicker diagnosis of the source of GI bleeding and may be able to receive a more definitive treatment of their bleeding source which could lead to a decreased length of hospital stay as well as fewer procedures.

17) Vulnerable Populations*

No vulnerable populations are expected to be enrolled.

18) Multi-Site Research*

Not applicable – single site research.

19) Community-Based Participatory Research*

Not applicable – not community-based participatory research.

20) Sharing of Results with Subjects*

Study results are not expected to be shared with individual subjects and subjects will not be identified in any publications; however, de-identified results may be published in publicly-available journals.

21) Setting

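### Section 15 says retention risk is equal in both groups and that early deployment carries no anticipated risk; this can hold per capsule swallowed but not per randomized subject

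*Protocol*

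**What the plan says.** Protocol section 15 (Risks to Subjects) opens with a statement about the randomized arm: "There are no anticipated risks to subjects who are randomized to the early deployment of the capsule". It then names retention as the most significant capsule risk, puts it at about 1% of cases (range 1-13%, the upper figure from Crohn's disease patients), and says: "This risk is the same for both groups and there is no anticipated unforeseen risk with early deployment". The next sentence reads: "The risks do not change based on timing".

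Section 10 (Randomization) gives the capsule to all early-arm patients. In the conventional arm, only some patients "will receive the capsule as indicated by what is considered the standard workup". Where section 10 describes the conventional workup, it mentions standard-of-care capsule use alongside a prevalence: "estimated that 5-15% of patients will have small intestinal bleeding".

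Section 10 (Procedure) provides a prokinetic if the capsule is still in the stomach at 40-60 minutes and expects this in about 1 in 8 patients. Section 15 later adds: "Another potential risk to the subjects in the study relates to the prokinetic medications", and lists hazards that include AV block, neuroleptic malignant syndrome and ventricular tachycardia. It does not split them by arm.

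The SAP's outcomes include mortality, re-bleeding and readmission, but neither retention nor prokinetic events.

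**The concern.** A device risk can be equal for each device used and still be very unequal between two randomized groups that use the device at different rates. For most early-arm patients the strategy adds a capsule, and possibly a prokinetic dose, that they might not otherwise have received. It does more than move the same capsule earlier.

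The no-anticipated-risk sentence is worded per randomized subject, so it conflicts directly with the retention and prokinetic risks set out later in the same section. The same-for-both-groups sentence conflicts as well if it is read by randomized arm.

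At stake are an accurate statement of what randomization to early deployment entails, and a harm report that can show it. The SAP plans no comparison of these events by arm.

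**Working it through.** The documents give no capsule count, prokinetic count or retention risk by arm, so there is no figure of the plan's own to reproduce. The check is exposure arithmetic.

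**Inputs**
- Planned size (section 10): "80 subjects in the early capsule group and a comparable number in the conventional workup group"; for the conventional arm, "An equal number subjects [up to 80] will be randomized to the" conventional workup group.
- Early-arm capsule use: 100% (section 10, Randomization).
- Conventional-arm capsule use: not stated. The values below are assumptions.
- Retention: about 1% per capsule (section 15). The 13% figure is not used, because it comes from Crohn's disease patients and section 5 excludes inflammatory bowel disease.
- Prokinetic need: 1 in 8 (section 10, Procedure).

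**Assumed conventional-arm capsule use**
- 5% and 15%: the section 10 prevalence of small intestinal bleeding, taken as a proxy for use.
- 10.7%: 36/336, the site's earlier capsule use among all GI-bleeding patients (section 4).
- 16.3%: as above, but assuming that all 36 capsules went to NHGIB patients. Section 10 gives about 230 NHGIB cases among 350, so 336 × 230/350 = 220.8, and 36/220.8 = 16.3%.
- 25%: assuming a capsule after every pair of non-diagnostic upper endoscopy and colonoscopy, with the section 4 yields of 52.9% and 47% treated as independent: (1 − 0.529) × (1 − 0.47) = 0.25.

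**Capsules and retentions at 80 per arm**

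Early arm: 80 capsules; expected retentions 80 × 0.01 = 0.80; chance of at least one 1 − 0.99^80 = 55%.

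Conventional arm, with c = 80 × use:

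| Use | Capsules c | Ratio 80/c | Expected retentions 0.01c | Chance of at least one, 1 − 0.99^c |
|---|---|---|---|---|
| 5% | 4 | 20.0 | 0.04 | 4% |
| 10.7% | 8.6 | 9.3 | 0.09 | 8% |
| 15% | 12 | 6.7 | 0.12 | 11% |
| 16.3% | 13.0 | 6.1 | 0.13 | 12% |
| 25% | 20 | 4.0 | 0.20 | 18% |

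Per randomized subject, expected retention risk is 1% in the early arm and 0.05-0.25% in the conventional arm. The excess is 0.80 − 0.20 = 0.60 to 0.80 − 0.04 = 0.76 events per 80.

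At the SAP's minimum of 36 per group the ratios do not change. Expected retentions become 0.36 against 0.02-0.09, and the chance of at least one in the early arm is 1 − 0.99^36 = 30%.

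**Capsule-triggered prokinetic doses**

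Early arm: 80/8 = 10. Conventional arm: 4/8 = 0.5 to 20/8 = 2.5, if the 1-in-8 rate applies there too. The early share is 10/12.5 = 80% to 10/10.5 = 95%.

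This counts only doses triggered by the capsule. Suppose 10% of the conventional arm (8 patients) also received one of these drugs before endoscopy and nobody in the early arm did. At 5-15% capsule use, the early share of all doses would then fall to 10/(10 + 0.5 + 8) = 54% or 10/(10 + 1.5 + 8) = 51%. The 10% is illustrative; the documents give no such rate.

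**The case against.** The strongest reply is that the same-for-both-groups sentence is about risk per capsule. It follows the statement that retention is the main capsule risk, precedes the sentence on timing, and leads to a rate per case. On that natural reading, unequal exposure does not contradict it. This stands for that sentence. It does not rescue the no-anticipated-risk sentence, which speaks of subjects by randomized arm.

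The second reply is that nothing is hidden. Section 10 states the unequal capsule use, section 15 gives the retention rate and the prokinetic hazards, and section 13 commits to following subjects for adverse events of medication and complications of the capsule. This also stands. The fault is inconsistent wording and a missing tabulation, not concealment.

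Several stronger readings are tempting but unsupported:
- A reader might infer that the protocol's own figures give a 7- to 20-fold difference in capsules. They do not: 5-15% is a prevalence of bleeding, and section 4 says capsules often follow negative endoscopies, so use could be higher.
- A reader might infer that nearly all prokinetic doses fall in the early arm. Sections 10 and 15 describe these drugs as in common or frequent use before upper endoscopy, without a rate. Section 29 mentions their cost only for the early group, but that is about billing and does not show that other patients receive none.
- A reader might infer that equal risk is the premise for safety review by study staff. Section 13 rests that review on an expectation of few adverse events, not on equality between arms.

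**Conclusion.** The point holds in a limited form. Section 15 is defensible per capsule swallowed but not per randomized subject, and its no-anticipated-risk sentence is inconsistent with the risks that follow it. The direction is certain as long as capsule use in the conventional arm stays below 100%, which section 10 states.

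The size is less certain. The 4- to 20-fold capsule ratio rests on an assumed 5-25% conventional-arm use. The 0.8 against 0.04-0.2 expected retentions rest also on 80 per arm and 1% per capsule in both arms. The prokinetic contrast holds only for capsule-triggered doses.

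The absolute retention excess is under one event, and section 15 describes decompensation that needs intervention as extremely rare. The documents do not show that an early-arm excess would be dismissed as chance, since the exposure difference is stated. The consent text is not available here, so it cannot be called wrong. No endpoint, sample size or efficacy analysis is affected. Severity: minor.

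**What to change.** In section 15, say that the risk per capsule is expected to be the same in both arms, but that exposure is higher in the early arm. The risk per randomized subject is therefore higher there for retention and for capsule-triggered prokinetic use. Reconcile the no-anticipated-risk sentence with the retention and prokinetic paragraphs, and check the consent text for consistency.

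Add one safety table to the SAP covering:
- retention;
- prokinetic use, with capsule-triggered and pre-endoscopy doses shown separately;
- related adverse events.

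Report each by randomized arm, with all randomized subjects as the denominator, and the capsule-related rows also per capsule swallowed.

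Do not enter 5-15% capsule use, or prokinetic counts derived from it, in the protocol as expectations. The first would turn a prevalence into a usage rate, and the second would leave out pre-endoscopy doses.

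The cost is a few sentences and one table. Section 10 (Review and Follow-Up) does not name medication administration among the recorded items, so prokinetic use may need chart abstraction. That would have to be done before the identifier keys are destroyed under section 12. The downside is that the stated early-arm risk becomes slightly less favourable. No dose, clinical rule or design element changes.

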In patients with hematemesis, upper endoscopy remains the diagnostic and therapeutic modality of choice. However patients with melena and hematochezia may benefit from early VCE since both signs and symptoms provide poor localization as to the origin of bleeding. Data from our previous study suggests that the ingestion of a video capsule in the emergency department could quickly and non-invasively provide clinicians accurate data as to the origin of the bleeding. This information could provide a guide to further management of the patient. Video capsule endoscopy is able to visualize bleeding in the esophagus, stomach, duodenum, small intestine and right colon, thereby eliminating the guess work of deciding which endoscopic approach to use.

At UMass, we have shown that of the 36 patients who received a video capsule, 26 (72.2%) had diagnostic studies (i.e. bleeding was identified). In comparison, 152 patients required upper endoscopy (of which 52.9% were diagnostic) and 64 patients required colonoscopy (of which 47%

INVESTIGATOR STUDY PLAN - REQUIRED

were diagnostic). Of those 26 patients with diagnostic capsule studies, 13 also required upper endoscopy, 1 required a colonoscopy, and 4 required both a colonoscopy and endoscopy. It is important to recognize, however, that often capsule studies are performed AFTER upper endoscopy and colonoscopy and performed and are negative. This sequence is the conventional work up of bleeding. Despite being performed later in the hospital course of our patients, capsule studies have a high diagnostic yield. In reality VCE is used uncommonly in acute bleeding because it is rarely considered in the context of acute GI bleeding

In this study, we propose the approach of using the video capsule as the first diagnostic test PRIOR to colonoscopy and endoscopy; this may lead to a shortened time to diagnosis, a reduction in length of stay, and a reduction in numbers of procedures due to early, accurate localization of the source of bleeding. All of these components could result in better quality of care and cost containment.^{1,2} Further, it is known that 80% of patients stop bleeding spontaneously. Thus the earlier they are examined the more likely the origin of the bleeding is likely to be found

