Subjects will be only providing health information to the investigators in this study. They will be offered an opportunity to ask any questions they have regarding this study. All information that will be used for analysis in this study that utilizes patient health information will be password-encrypted and de-identified. HIPAA Authorization to Disclose will be obtained from subjects prior to enrollment in the study.

28) Compensation for Research-Related Injury

In the unlikely event of a research-related injury, subjects or their insurance will be responsible for coverage.

The only complication of capsule endoscopy, apart from inability of the patient to swallow the device, is true capsule retention [>> 2 weeks of retention] with or without obstruction. In this case it is the underlying disease causing the problem and the management would be covered by the patient's insurance.

29) Economic Burden to Subjects

None is anticipated from participating in the study. All costs associated with the emergency department stay, hospital admission and associated testing (including but not limited to endoscopy procedures) will be paid by the subject or insurance and the subject will be responsible for all co-pays, deductibles, etc. These are all standard of care procedures.

The patients recruited to be subjects in this study would most likely require admission to the hospital or the clinical decision unit until a thorough evaluation is completed to determine the source of bleeding. This is a clinical decision that will be made regardless of participation in this study, based on the clinical judgment of the attending physician in the emergency department.

For those in the early capsule group, the cost of using the prokinetic medications (if necessary) will also be paid by the subject or insurance as this is part of the standard of care procedures for their emergency department admission and assessment. Any subsequent intervention will be billed to the subject or insurance.

INVESTIGATOR STUDY PLAN - REQUIRED

The cost of the video capsule and its reading, both for the early capsule group and any subject in the standard of care group who receives a video capsule, will be paid for by the study and not billed to the subject or insurance.

30) Consent Process

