Consent will take place in the Emergency Department. Subjects will be given as much time as they require before making a decision to provide consent. The time provided for discussing the consent process with subject will be 15 minutes or greater as the subject requires. Only the listed study staff members will be involved in the consent process. In order to minimize the possibility of coercion during the consent process, potential subjects will be notified that their care will not be altered in any way if they choose to provide or not provide consent. Also, to ensure subjects' understanding we will only recruit English-speaking subjects for this study.

31) Process to Document Consent in Writing

We will be following "SOP: Written Documentation of Consent."

32) Drugs or Devices

The video capsule that will be used in this study is the Olympus small intestinal capsule endoscopy system (EC-10 System). This system has been cleared by the FDA under 510(k) approval number K123421. This is a capsule imaging system intended for visualization of the small intestine mucosa. This is the FDA cleared labeling. There is no requirement for timing in the FDA labeling. The video capsules will be locked in our study coordinator's office. Handling and administration of the capsules will be performed by study staff members who have been trained and have experience in the tasks related to the video capsules.

A copy of the clearance document and a product manual have been added to the attachments for this study.

The two prokinetic agents that will be used as part of this study if capsule retention occurs are metoclopramide and erythromycin. Package inserts for both medications are included as attachments to this study. Metoclopramide is labeled for use in gastroparesis and not gastrointestinal bleeding. Erythromycin is not approved as a prokinetic agent; however, both drugs are often used in the hospital setting for the purposes of emptying the stomach of blood in patients with gastrointestinal bleeding.

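### Section 30 has staff tell patients that care is the same whether or not they consent; the protocol's own procedures contradict this for the early-capsule arm (minor wording correction)

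*Protocol*

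**What the plan says.** Protocol Section 30 (Consent Process), in a sentence whose declared aim is to limit coercion, states that "potential subjects will be notified that their care will not be altered in any way if they choose to provide or not provide consent".

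Other sections describe what follows consent:

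- Section 4 (Background) proposes "using the video capsule as the first diagnostic test PRIOR to colonoscopy and endoscopy".
- Section 15 (Risks to Subjects) says "This study is investigating the benefits of re-ordering the process of the current care algorithm for NHGIB".
- Section 10 (Randomization) has consent precede allocation. For the early-capsule arm it says "this group of subjects will have a VCE deployed as soon as possible after presentation to the ED", once eligibility and preparation are settled. A patient who has eaten waits until 10 hours after the last meal.
- Section 10 (Procedure) adds real-time viewer checks, a prokinetic if the capsule is still in the stomach at 40 to 60 minutes, and a recommended next test that depends on the finding. If the capsule is non-diagnostic, no blood is seen and hematochezia is not continuing, "the subject will be placed in ED observation for up to 23 hours and evaluated for potential discharge".

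On cost, Section 29 (Economic Burden to Subjects) opens with "None is anticipated from participating in the study". It later says that for the early-capsule group "the cost of using the prokinetic medications (if necessary) will also be paid by the subject or insurance", and gives as the reason that this is standard of care. The study pays for the capsule and its reading in both arms.

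**The concern.** The Section 30 sentence covers both choices, consenting and declining. An assurance against penalty needs only the second. By including the first, the protocol directs staff to say something that its own procedures make untrue for roughly half of those who agree.

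What is at stake is the accuracy of the consent discussion. It takes place in an emergency department and is planned to last at least 15 minutes. This is the only specific statement in the documents about what patients will hear on how consent affects their care. It also sits badly with Section 16, which offers earlier diagnosis, fewer procedures and a shorter stay as possible benefits of the early-capsule arm. Those benefits could not arise if care were unchanged.

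Section 29 raises a smaller version of the same problem: a flat denial of cost, followed by a charge that arises from the early-capsule pathway.

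**Working it through.** The plan states no figure to reproduce on this point. The check is mainly a comparison of passages, with one count.

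**1. Declining.** The patient is not randomized and receives usual care. The Section 30 sentence is correct.

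**2. Consenting, conventional arm (up to 80).** Workup follows usual practice under Section 10. For the diagnostic pathway, the sentence is close to correct.

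**3. Consenting, early-capsule arm (up to 80).** Five elements follow the study algorithm in Section 10:

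- the first test (capsule before endoscopy or colonoscopy);
- its timing (at once, or 10 hours after the last meal);
- a prokinetic, if the capsule has not left the stomach;
- the recommended next test, set by the capsule finding;
- observation and discharge evaluation after a negative capsule. Conventional-arm patients are instead discharged on the hospitalist's recommendation once treatment is complete.

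The sentence is incorrect for this arm.

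**4. Expected prokinetic use.** Inputs are n = 80 (Section 10, Randomization) and p = 1/8 (Section 10, Procedure, given there as based on experience).

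- Expected number: n × p = 80 × 1/8 = 10.
- 95% binomial range for n = 80, p = 1/8: 5 to 16.
- Probability of at least one: 1 − (7/8)^80 = 0.99998.

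If 1 in 8 is about right, some early-arm patients or their insurers will almost certainly be billed for a prokinetic.

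**5. How the prokinetic is described.** Section 29 calls it standard of care and bills it accordingly. Section 15 describes a single dose given for study purposes, and Section 32 lists both agents as used within the study. Section 32 also notes that metoclopramide is not labeled for gastrointestinal bleeding and that erythromycin is not approved as a prokinetic. These descriptions need to be reconciled.

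**The case against.** The best defense is that the sentence is the customary promise that refusal carries no penalty. Its opening words about coercion support that reading, which is probably what the authors meant. This bears on severity, but the wording expressly includes patients who do consent, so it remains inaccurate.

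The defense is right on several stronger readings that a reader might infer:

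- **That patients are kept uninformed.** This is not shown. The consent form is not among the documents, Section 23 confirms that one exists, and Section 24 says risks and benefits will be explained. The IRB is not misled either, since the same protocol sets out the full algorithm, the drug risks and the labeling status.
- **That patients would learn the truth after allocation and withdraw mainly from the early arm.** Nothing in the documents supports either step.
- **That the admission statement in Section 29 is false.** It says "This is a clinical decision that will be made regardless of participation in this study", and Section 5 makes a plan to admit an entry criterion, so that decision precedes consent. Section 10 concerns what happens after a completed capsule study, and speaks only of evaluation for possible discharge.
- **That about 22 of 80 would enter the observation branch.** One could take the 10 non-diagnostic capsules of 36 in Section 4 (27.8%) and multiply by 80. Those capsules were often given after negative endoscopy and colonoscopy, not as the first test, and the branch also requires no continuing hematochezia. The figure does not carry over.
- **That a cost is hidden.** Section 29 discloses the prokinetic billing, and the study pays for the capsule and its reading, so the net cost to a patient could go either way. Section 15 also notes that these drugs are already often used before endoscopy in upper GI bleeding, so the 10 are recipients and not necessarily 10 added exposures.

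**Conclusion.** The point holds as a contradiction between a scripted statement and the protocol's own procedures. The Section 30 sentence is right for patients who decline and wrong for those who consent and are allocated to the early capsule, up to 80 of 160. About 10 of those 80 (range 5 to 16) would receive a prokinetic, assuming that the protocol's 1 in 8 applies to this arm. In Section 29, what remains is the clash between a flat denial of economic burden and the billing that follows it, together with the inconsistent description of the prokinetic.

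Severity is minor. No harm to patients' understanding is demonstrated, and no sample size, power or analysis figure is affected. It is still worth correcting, because staff who follow Section 30 as written would make an inaccurate statement, and the correction is cheap.

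**What to change.** **Section 30.** Replace the sentence with two statements. First, declining will not affect usual care. Second, those who consent are assigned by chance to conventional workup or to an early-capsule pathway, in which the first test, its fasting wait, possible prokinetic use, the recommended next test, and observation or discharge evaluation follow the study. Check that the consent form says the same.

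**Section 29.** Replace the opening denial with a statement that the study pays for the capsule and its reading in both arms, while any prokinetic is billed to the subject or insurance. Reconcile the standard-of-care description there with Sections 15 and 32, which present the prokinetic as given for the study.

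**Cost.** One IRB modification covering a few sentences, and possibly a slightly lower agreement rate. These edits change no procedure, sample size or analysis.
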